8.2.4 Relationship to Investigational Product and Relationship to Study Procedures

The Investigator must assess the causal relationship between the exposure to the IP (P4M3 Gen 2.0 and cigarettes) and each of the reported AEs, using the classification system and the criteria described below. The same assessment must be made separately to assess the causal relationship between the study procedures and each of the reported AEs:

Not related: The temporal relationship of the adverse event to IP administration or study procedure(s) makes a causal relationship unlikely, or concomitant medication, therapeutic interventions, or underlying conditions provide a sufficient explanation for the observed event.

Related: The temporal relationship of the adverse event to IP or study procedure(s) makes a causal relationship possible, and concomitant medication, therapeutic interventions, or underlying conditions do not provide a sufficient explanation for the observed event.

8.2.5 Expectedness

Any AE assessed as related to the IP (P4M3 Gen 2.0 or cigarettes) will be assessed for its expectedness. An AE will be regarded as “unexpected” if its nature or severity is not consistent with information already recorded in section 6.5 of the current Investigator’s Brochure [5].

Confidentiality Statement

Data and information contained in this document are considered to constitute trade secrets and confidential commercial information, and the legal protections provided to such trade secrets and confidential information are hereby claimed under the provisions of applicable law. No part of this document may be publicly disclosed without the written consent of Philip Morris Products S.A.

8.2.6 Follow-up of Non-serious and Serious Adverse Events

Any non-serious AE that is ongoing at the time of Discharge or early termination will be followed-up by the Investigator during the Safety Follow-Up Period until it has been resolved, stabilized (i.e., no worsening of the condition), or an acceptable explanation has been found (e.g., a chronic condition). The follow-up of the ongoing non-serious AEs will be done via a phone call performed at the end of the Safety Follow-Up Period. If the subject is not responding at the first phone call additional two attempts will be made, then subject will be declared lost to follow-up.

At the end of the 3-day Safety FU Period, all ongoing non-serious AEs will have the outcome documented as “unknown” and will not be followed-up by the Investigator. At the discretion of the Investigator, the subject will be referred to his General Practitioner to have his/her ongoing AEs addressed accordingly.

All SAEs will be followed up by the Investigator or designee after the end of the Safety Follow-Up Period, until their resolution, stabilization (i.e., no worsening of the condition), or an acceptable explanation has been found (e.g., a chronic condition). In case the subject cannot be reached for additional information related to SAE(s), a total 3 attempts should be performed before the subject will be declared as lost to follow-up.

8.3 Reporting of Serious Adverse Events

Any SAE observed during the period of collection in this study must be reported within 24 hours of first awareness to Sponsor, via email, having the SAE form attached as detailed in the Safety Management Plan (SMP).

As further information regarding an already reported SAE becomes available to any of the parties involved in this study, such follow-up information should be reported on a new SAE report form, marked as a follow-up report and submitted to Sponsor according to the same timelines as described above. The follow-up SAE report form must include the minimum information required for form completion and only changed/new information needs to be specified. Information provided in the follow-up SAE report form supersedes any information that was initially reported.

The SAE report form to be used in this study is provided as a separate document. All SAEs will also be recorded on the relevant CRF page, in addition to the SAE report form.

The Investigator or designee is responsible for submitting the relevant reports of SAEs that occur during the study to the IRB, according to local regulations and in accordance with the respective safety management plan (SMP).

Confidentiality Statement

Data and information contained in this document are considered to constitute trade secrets and confidential commercial information, and the legal protections provided to such trade secrets and confidential information are hereby claimed under the provisions of applicable law. No part of this document may be publicly disclosed without the written consent of Philip Morris Products S.A.

8.4 Reporting of Other Events Critical to Safety Evaluations

8.4.1 Abnormal Results of Laboratory Tests

Any clinical safety laboratory test result that is outside of the normal reference range will be reviewed by the Investigator and assessed for clinical significance according to its severity. The severity of abnormal laboratory test result must be assessed using Common Terminology Criteria for Adverse Events (CTCAE) version 5.0 grading scales ([Appendix C](#)). Whenever that grading scheme is not available for the laboratory result of concern, the Investigator should assess the severity and the clinical significance of that result using his/her medical judgment.

Abnormal laboratory test results detected at the Screening Visit whose CTCAE grades are 2 or higher or still are CTCAE grade 1 and deemed clinically significant are usually concomitant disease or a manifestation of one and must be recorded accordingly.

However, in some instances, they may be assessed as AEs (and therefore must be handled as described in section [8.2](#)) or as manifestations of already reported AEs. This decision will require a careful assessment of the abnormal result within the clinical context on a case-by-case basis and will depend on the Investigator's medical judgment.

Abnormal laboratory test results detected after the Screening Visit whose CTCAE grades are 2 or higher or still are CTCAE grade 1 and deemed clinically significant must either be recorded as AEs (and handled as described in section [8.2](#)) or linked to a concomitant disease or to an already reported AE.

The principles for assessing and reporting abnormal laboratory test results, emerging after the Screening Visit, using CTCAE 5.0 grading scales are set up in [Table 5](#):

Table 5 Principles for Assessing and Reporting Abnormal Laboratory Test Results

Grading	Clinically significant?	Is it a grade increase from previous results in study?	Report?
Grade 1	No	Not applicable	No
Grade 1	Yes	No	No*
Grade 1	Yes	Yes	Yes, as AE or linked to an already reported AE
Grade 2 or higher	No/Yes	No	No*
Grade 2 or higher	No/Yes	Yes	Yes, as AE or linked to an already reported AE

* in this situation, this abnormal lab test result is either a manifestation of a concomitant disease or of an already reported AE.

Confidentiality Statement

Data and information contained in this document are considered to constitute trade secrets and confidential commercial information, and the legal protections provided to such trade secrets and confidential information are hereby claimed under the provisions of applicable law. No part of this document may be publicly disclosed without the written consent of Philip Morris Products S.A.

In general, laboratory values will be recorded as “increased <lab parameter>” or “decreased <lab parameter>” to ensure consistency of recording/coding.

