2.3.2 Anticipated Foreseeable Risks due to Study Procedures

The risk of scheduled procedures in the present study (e.g., blood samples) are deemed to be on par with procedures routinely performed during normal or extended health examinations by the subject's healthcare professional. The total volume of blood to be drawn is approximately 300 mL and does not exceed the levels for a standard blood donation. The risks related to blood sampling include for example: excessive bleeding, fainting, hematoma, paresthesia or infection, and those related to the total amount of blood taken over a period of time such as weakness, dizziness or anemia.

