8.4.2 Reporting other abnormal findings

The other abnormal findings discovered during different clinical assessments (e.g., ECG, spirometry, physical examination, vital signs, body weight) should be evaluated for clinical significance by the Investigator/designee based on his/her medical judgement. All abnormal clinically significant test results or clinical examination findings should be reported as AEs and handled as described in section 8.2.

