APPENDIX C ABNORMAL LABORATORY VALUES GRADING

Abnormal Laboratory Values Rating: Clinical Chemistry Parameters

Serum Chemistry	Mild (Grade 1)	Moderate (Grade 2)	Severe (Grade 3)	Life-Threatening (Grade 4)
Sodium – Hyponatremia (mmol/L)	<LLN - 130	125-129 mmol/L and asymptomatic	125-129 symptomatic; 120-124 regardless of symptoms	<120
Sodium – Hypernatremia (mmol/L)	>ULN - 150	>150 - 155 intervention initiated	>155 - 160; hospitalization indicated	>160
Potassium – Hyperkalemia (mmol/L)	>ULN - 5.5	>5.5 - 6.0 intervention initiated	>6.0 - 7.0; hospitalization indicated	>7.0
Potassium – Hypokalemia (mmol/L)	<LLN - 3.0	<LLN - 3.0; symptomatic; intervention indicated	<3.0 - 2.5; hospitalization indicated	<2.5
Glucose – Hypoglycemia (mg/dL) (mmol/L)	<LLN – 55; <LLN – 3.0	<55 – 40; <3.0 – 2.2	<40 – 30; <2.2 – 1.7	<30; <1.7
Glucose – Hyperglycemia:	Abnormal glucose above baseline with no medical intervention	Change in daily management from baseline for a diabetic; oral antiglycemic agent initiated; workup for diabetes	Insulin therapy initiated; hospitalization indicated	Life-threatening consequences ; urgent intervention indicated
Creatinine increased	>ULN – 1.5 x ULN	>1.5 – 3.0 x Baseline; >1.5 – 3.0 x ULN	>3.0 x Baseline; >3.0 – 6.0 x ULN	>6.0 x ULN
Albumin - Hypoalbuminemia (g/dL) (g/L)	<LLN – 3; <LLN - 30	<3 – 2; <30 - 20	<2; <20	Life-threatening consequences

Confidentiality Statement

Data and information contained in this document are considered to constitute trade secrets and confidential commercial information, and the legal protections provided to such trade secrets and confidential information are hereby claimed under the provisions of applicable law. No part of this document may be publicly disclosed without the written consent of Philip Morris Products S.A.

Serum Chemistry	Mild (Grade 1)	Moderate (Grade 2)	Severe (Grade 3)	Life-Threatening (Grade 4)
Alkaline phosphatase increased	>ULN - 2.5 x ULN if >	>2.5 – 5.0 x ULN	>5.0 – 20.0 x ULN	>20.0 x ULN
ALT / AST increased	>ULN – 3.0 x ULN	>3.0 – 5.0 x ULN	>5.0 – 20.0 x ULN	>20.0 x ULN
Gamma-glutamyl transferase (GGT) increased	>ULN – 2.5 x ULN	>2.5 – 5.0 x ULN	>5.0 – 20.0 x ULN	>20.0 x ULN
Lactate dehydrogenase (LDH) increased	>ULN	-	-	-
Blood bilirubin increased (total and direct)	>ULN – 1.5 x ULN	>1.5 – 3.0 x ULN	>3.0 – 10.0 x ULN	>10.0 x ULN
Cholesterol high (mg/dL) (mmol/L)	>ULN - 300; >ULN - 7.75	>300-400; >7.75-10.34	>400-500; >10.34-12.92	>500; >12.92

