Listing 15.3.4.3.2 Out-of-Range Values and Recheck Results - Clinical chemistry (Safety Population)

Subject Number	Age/ Study Sex Period Day			Date	Time	Fast?	Parameter1 <Range> (Unit)	Parameter2 <Range> (Unit)	Parameter3 <Range> (Unit)	Parameter4 <Range> (Unit)	Parameter5 <Range> (Unit)
	1	X	XX/X	Screen	.	.	XX	XX HN	XX LNG1	XX LN	XX HN
X	XX/X	Screen	.	DDMMYYYY	HH:MM:SS	XX	XX HN				
	1	X	XX/X	DDMMYYYY	HH:MM:SS	XXX		XX LNG1	XX LN		

Age is calculated from the date of informed consent. F = Female, M = Male

H = Above normal range, L = Below normal range

PI Interpretation: N = Not clinically significant, Y = Clinically significant

CTCAE grade: G1 = Mild, G2 = Moderate

Fast? = Did the subject fast at least 10 hours?

Program: /CAXXXX/sas_prg/stsas/tab_PROGRAMNAME.sas DDMMYYYY HH:MM Status: DRAFT (Page X of Y)

Programmer Notes: Replace Parameter1, 2 etc. with actual lab tests in the study. Sort unscheduled assessment and early termination chronologically with other scheduled assessments and rechecks. Recheck should be sorted with the scheduled time point the recheck is for Listing 15.3.4.3.4 and 15.3.4.3.6 will resemble 15.3.4.3.2. Fast? column will only be presented for serum chemistry.

Programmer Notes: Clinically significant lab values generally will be captured as AEs. Derive an additional CS flag for PI flag (+) based on positive comments (i.e. CS/Clinically Significant). Present this derived 4th column in all tables, and list only subjects/tests which are PI-determined clinically significant lab values in Table 15.2.6.4.4.

Philip Morris Products S.A.
P4M3 Gen 2.0, P4-PK-04-US

████████ Statistical Analysis Plan Number CA34617

Listing 15.3.4.3.7 will have the following format:

Listing 15.3.4.3.7 Clinically Significant Values and Recheck Results (Safety Population)

Subject Age/ Number	Study Sex	Period	Day	Date	Time	Department	Test	Result	Normal Range	Unit
X	XXX	1	X	DDMMYYYY	HH:MM:SS	XXXXXXXXXXXXXX	XXXXXXXXXXXX	XXX HY XXX	X-X X-X	mg/dL mg/dL
			X	DDMMYYYY	HH:MM:SS	XXXXXXXXXXXXXX	XXXXXXXXXXXX			

F = Female, M = Male

H = Above normal range

PI Interpretation: Y = Clinically significant

Program: /CAXXXX/sas_prg/stsas/tab_PROGRAMNAME.sas DDMMYYYY HH:MM Status:DRAFT (Page X of Y)

Programmer Note: All time points for a subject/test with at least one value deemed as CS by the PI will be presented in this table.

If no event meet these criteria then include a statement as follows:

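### Table 5 of Protocol 8.4.1 contradicts the section's text for one case: a Grade 1 laboratory result that was not clinically significant, stays Grade 1, and is later judged clinically significant

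*Protocol*

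**What the plan says.** The text of Protocol 8.4.1 sets the rule for laboratory results found after Screening. Results of Grade 2 or higher "or still are CTCAE grade 1 and deemed clinically significant must either be recorded as AEs", "or linked to a concomitant disease or to an already reported AE". At Grade 1 the trigger is clinical significance; no rise in grade is required. The same section applies the same threshold at Screening, so a Grade 1 result that is not clinically significant creates no record there.

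Table 5 of the same section adds a second condition, whether the grade has risen since earlier study results. A Grade 1 result that is not clinically significant is not reported (row 1). One that is clinically significant without a grade rise gets a starred No (row 2), and with a rise a Yes (row 3). At Grade 2 or higher, no rise gives a starred No and a rise gives a Yes. The footnote explains the star: "in this situation, this abnormal lab test result is either a manifestation of a concomitant disease or of an already reported AE".

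SAP 14.5, in a programmer note to the laboratory listings, expects that "Clinically significant lab values generally will be captured as AEs".

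**The concern.** Row 2 and its footnote say no report is needed because a record already exists. If the earlier result was Grade 1 and not clinically significant, neither the Screening rule nor row 1 would have created one. The text then asks for a record or a link, the table asks for nothing, and there is nothing to link to.

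The situation is plausible. Exclusion criterion 3 leaves laboratory abnormalities to the Investigator's judgment, so subjects can enter with non-significant Grade 1 values. In Appendix C, "Lactate dehydrogenase (LDH) increased" and urine glucose have a Grade 1 entry only, so once such a test is abnormal no later change can raise its grade.

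Adverse event incidence is a secondary endpoint, and Protocol 2.1.2 states that the product has not been used in humans before. Protocol 12.6.6 plans a summary of laboratory adverse events and assigns those found on Day 3 to the product used the day before. A result not recorded as an event also receives no causality assessment (8.2.4) and no adverse event follow-up (8.2.6).

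**Working it through.** The plan gives no figure to reproduce; this is a check of reporting logic. CS means judged clinically significant.

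**Inputs**
- Text rule, at and after Screening (8.4.1): a record or link is needed for Grade 2 or higher, or Grade 1 with CS.
- Table 5 rows as described above.
- Appendix C: ALT Grade 1 runs from above ULN to 3.0 x ULN; LDH has Grade 1 only; anemia has Grades 1 to 4, with Grade 1 from LLN down to 10.0 g/dL.
- Scheduled safety laboratory draws (SAP 10.8): Screening, Day -1, Day 3.

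**One example.** ALT is 1.1 x ULN on Day -1, not CS, then 2.9 x ULN on Day 3, CS. Since 1 < 1.1 < 2.9 < 3.0, both are Grade 1.

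| Rule | Day -1 result | Day 3 result |
|---|---|---|
| 8.4.1 text | No record needed | Record as an event, or link |
| Table 5 | Row 1: not reported | Row 2: starred No |
| Footnote premise | n/a | Needs an earlier record; none exists |

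**All transitions.** A test with k grades has 2k + 1 states: normal, and each grade with or without CS. That gives (2k + 1)² pairs of earlier and current state. The text requires action for every current state except normal and Grade 1 without CS, that is, 2k - 1 states.

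| | LDH (k = 1) | Anemia (k = 4) |
|---|---|---|
| Transitions | 3² = 9 | 9² = 81 |
| Text requires record or link | 1 x 3 = 3 | 7 x 9 = 63 |
| Table 5 Yes | 1 | 1 + 2x3 + 2x5 + 2x7 = 31 |
| Table 5 starred No | 3 - 1 = 2 | 63 - 31 = 32 |
| Starred No with no earlier record | 1 | 1 |

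The last row follows directly. Only two earlier states leave no record: normal, and Grade 1 without CS. From normal, any graded result is a rise, so it is never a starred No. From Grade 1 without CS, a starred No arises only if the result stays Grade 1 and becomes CS. The other starred outcomes (1 for LDH, 31 for anemia) fit the footnote.

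**Across the three draws**, the paths that reach this case on Day 3 with nothing recorded before are:
- normal, then Grade 1 without CS, then Grade 1 with CS;
- Grade 1 without CS twice, then Grade 1 with CS;
- Grade 1 without CS, then normal, then Grade 1 with CS, but only if the comparison is with the highest earlier grade. Table 5 does not say whether it means the last or the highest.

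**The case against.** The strongest defence is that the rest of the protocol still calls for capture. Table 5 is headed as principles, whereas the text is mandatory. The adverse event definition in 8.1.1 includes worsening of an existing condition, and 8.1.3 asks that increased severity of a concomitant disease be captured. The values also survive elsewhere: change from baseline in laboratory parameters is a separate secondary endpoint, and SAP Listing 15.3.4.3.7 shows clinically significant values whatever their adverse event status. All of this stands. It makes the loss possible rather than certain, but it does not make the table agree with the text.

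Several stronger readings are tempting and are not supported:
- *All LDH rises are lost.* An LDH value going from normal to above ULN is a rise to Grade 1 and is reported if CS. Only LDH already above ULN and previously judged not significant is caught.
- *Most anemia is lost.* Protocol 2.3.2 does name "those related to the total amount of blood taken over a period of time such as weakness, dizziness or anemia" among the risks of blood sampling, but new clinically significant anemia and any move to a higher grade from Grade 2 up are reported. The documents give neither an LLN nor an incidence. For an assumed LLN of 11.5 to 13.5 g/dL, the Grade 1 band is LLN - 10.0 = 1.5 to 3.5 g/dL wide. That caps a within-grade fall; it is not a range the table hides.
- *All within-grade worsening is lost.* From Grade 1 with CS, or from Grade 2 or higher, the text already has a record to link to.
- *Sites will differ.* The study is single-center; the question is which rule its assessors apply.
- *8.4.2 settles it.* Its sentence "All abnormal clinically significant test results or clinical examination findings should be reported as AEs" concerns ECG, spirometry, physical examination and similar findings. It helps only by analogy.

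The SAP note says generally, so it states an expectation and not a rule.

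**Conclusion.** The contradiction is real and confined to one transition: Grade 1 without clinical significance to Grade 1 with it. There the text requires a record or link, and Table 5 declines a report by pointing to a record that need not exist. The conclusion assumes that the earlier non-significant result was left unrecorded, as both rules allow. Loss from adverse event incidence further requires that the site follow the table rather than the text. Where that happens, SAP Listing 15.3.4.3.7 can show a significant value with no matching event. How many subjects this would touch cannot be derived from the documents. The pharmacokinetic main objective is not affected. It should be corrected because it is a stated rule bearing on a secondary safety endpoint for a product new to humans.

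**What to change.** Reconcile Table 5 with the 8.4.1 text:
1. In the two Grade 1 clinically significant rows only, make the trigger a grade increase or new clinical significance compared with previous results. Do not extend this to the Grade 2 or higher rows: with the present Yes wording it would call for an event, or a link to one, where the text lets the result be tied to a concomitant disease.
2. Allow the starred No only where a concomitant disease or adverse event is already recorded and the result is linked to it.
3. Add linking to a concomitant disease as an option in the Yes rows, as the text already permits.
4. State whether previous results means the last or the highest earlier grade.

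The failing transition then moves to a Yes row, and no starred No remains without a record behind it. The cost is a few cells and a footnote in one table, plus a line in site training. The downside is that a few more laboratory adverse events may be recorded.

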8.4.2 Reporting other abnormal findings

The other abnormal findings discovered during different clinical assessments (e.g., ECG, spirometry, physical examination, vital signs, body weight) should be evaluated for clinical significance by the Investigator/designee based on his/her medical judgement. All abnormal clinically significant test results or clinical examination findings should be reported as AEs and handled as described in section 8.2.

8.5 Reporting and Follow-Up of Pregnancies

8.5.1 Period of Collection and Follow-up

Pregnancies detected between the time of signature of the ICF and the time before first exposure to the IP will be considered a reason for screen failure. No pregnancy form will be filled in that case, however the diagnosed pregnancy must be captured in the screen failure page of the CRF.

In case of pregnancies detected between enrollment and prior to randomization, subject will be discontinued, and reported as “enrolled but not randomized” subject. Early termination procedures shall apply. No pregnancy form will be filled.

Any pregnancy detected after randomization must be reported by the Investigator within 24 hours. This also includes pregnancies spontaneously reported to the Investigator after the end of the study for a subject. A dedicated pregnancy form will be used to report reportable cases of pregnancy.

Any pregnancy that was potentially associated with exposure to IP (P4M3 Gen 2.0 or cigarette) will be followed-up until an outcome is reached (e.g., normal delivery, spontaneous abortion, or voluntary termination) and also until 8 weeks after delivery. Any pregnancy complication, adverse pregnancy outcome or maternal complications will be recorded as an AE accordingly.

The procedure outlined in section 8.3 should be followed to collect pregnancy reports and provide any additional/follow-up information to Sponsor.

Confidentiality Statement

Data and information contained in this document are considered to constitute trade secrets and confidential commercial information, and the legal protections provided to such trade secrets and confidential information are hereby claimed under the provisions of applicable law. No part of this document may be publicly disclosed without the written consent of Philip Morris Products S.A.

